**SECTION I - MEDICAL HISTORY**

**READ and HEARD:** *In the next set of questions we will ask about some medical treatments you may have had.*

I1. Have you ever had a blood transfusion? (Choose one)

- 0 No **Skip to I5**
- 1 Yes
- 97 Don't Know
- 98 Refuse to Answer

I2. How many transfusion episodes have you had?

— —

- 97 Don't Know
- 98 Refuse to Answer

I3. When was the first year you received a transfusion?

— — — —

- 9997 Don't Know
- 9998 Refuse to Answer

**If I3 is less than B2 then READ and HEARD:** *"The year that you entered for first year transfusion is smaller than the year you were born. Please correct the year of your first transfusion." (Returns to I3)*

14. When was the last year you received a transfusion?

— — — —

9997 Don't Know

9998 Refuse to Answer

***If 14 is less than 13 then READ and HEARD: "The year that you entered for last year of transfusion is smaller than the year of your first reported transfusion. Please correct the last year of your transfusion." (Returns to 14)***

15. Have you ever had minor or major surgery in a hospital, doctor's room, or dentist's office? (Choose one)

0 No ***Skip to 19***

1 Yes

97 Don't Know

98 Refuse to Answer

16. In the 6 months before your donation, have you had minor or major medical surgery in hospital? (Choose one)

0 No

1 Yes

97 Don't Know

98 Refuse to Answer

17. In the 6 months before your donation, have you had any surgical procedures in your doctor's room or office? (Choose one)

- 0 No
- 1 Yes
- 97 Don't Know
- 98 Refuse to Answer

18. In the 6 months before your donation, have you had any tooth extractions or another dental procedure at a dentist's office? (Choose one)

- 0 No
- 1 Yes
- 97 Don't Know
- 98 Refuse to Answer

19. Have you ever had an endoscopy (a medical test where a flexible tube is used to look inside of your throat and digestive system) or colonoscopy (a medical test where tube is used to look inside your colon/large intestine)? (Choose one)

- 0 No **Skip to I11**
- 1 Yes
- 97 Don't Know
- 98 Refuse to Answer

I10. In the 6 months before your donation, have you had an endoscopy or colonoscopy? (Choose one)

- 0 No
- 1 Yes
- 7 Don't Know
- 8 Refuse to Answer

I11. Have you ever been immunized / vaccinated against Hepatitis B?

- 0 No
- 1 Yes
- 97 Don't Know
- 98 Refuse to Answer

I11b. If yes, can you tell us your age when you were immunized/vaccinated against Hepatitis B?

\_\_\_\_\_ years old

I12. In the 6 months before your donation, did you receive an injection from a traditional healer for any reason? (Choose one)

- 0 No
- 1 Yes
- 97 Don't Know
- 98 Refuse to Answer

## SECTION J- OTHER POTENTIAL RISK FACTORS

**READ and HEARD:** *The next set of questions will ask you about situations or activities that could be important for our research to improve blood safety at SANBS. Some of the questions cover topics that are very personal. Please respond as accurately as you can. You may skip any question you are not comfortable answering.*

J1. In the 6 months before your donation, have you spent three or more nights in jail, prison, or a detention centre? (Choose one)

- 0 No
- 1 Yes
- 97 Don't Know
- 98 Refuse to Answer

J2. In the 6 months before your donation, have you had acupuncture treatments? (Choose one)

- 0 No **Skip to J5**
- 1 Yes
- 97 Don't Know
- 98 Refuse to Answer

J3. Who performed the acupuncture treatments? (Check all that apply)

- 0 A registered health care professional (such as physiotherapist, chiropractor)
- 1 Chinese/ Asian healer
- 2 Traditional healer
- 3 Other
- 97 Don't Know

98 Refuse to Answer

J4. In the 6 months before your donation, how many times have you had acupuncture treatments?  
(Choose one)

1 1 time

2 2 to 5 times

3 5 or more times

97 Don't Know

98 Refuse to Answer

J5. How many tattoos do you have on your body? (Choose one)

0 0 (No tattoos) **Skip to J8**

1 1

2 2

3 3 or more

97 Don't Know

98 Refuse to Answer

J6. In the 6 months before your donation, have you gotten a new tattoo or had one re-applied? (Choose one)

0 No

1 Yes

97 Don't Know

98 Refuse to Answer

J7. Where did you get your most recent tattoo? (Choose one)

- 1 Tattoo parlor
- 2 Informal tattoo parlor (e.g. fleamarket or street fair)
- 3 At home, a friends place, or at parties/raves
- 4 Jail, prison or detention centre
- 5 Other
- 97 Don't Know
- 98 Refuse to Answer

J8. How many ear or body piercings do you have? (Choose one)

- 0 0 (No piercings) **Skip to J11**
- 1 1
- 2 2
- 3 3 or more
- 97 Don't Know
- 98 Refuse to Answer

J9. In the 6 months before your donation, have you had new ear or body piercings? (Choose one)

- 0 No
- 1 Yes
- 97 Don't Know
- 98 Refuse to Answer

J10. Where did you get your most recent piercing? (Choose one)

- 1 Pharmacy or medical clinic
- 2 Tattoo/piercing parlor
- 3 At home, a friends place, or at parties/raves
- 4 Informal ear-piercing (for example at a flea market or street fair)
- 5 Jail
- 6 Other
- 97 Don't Know
- 98 Refuse to Answer

J11. Have you ever had a manicure or pedicure at a beauty salon or had a shave at a barbershop?  
(Choose one)

- 0 No ***Skip to instruction before J14***
- 1 Yes
- 97 Don't Know
- 98 Refuse to Answer

J12. How many times have you had manicures or pedicures or shaves at a beauty salon or barbershop?  
(Choose one)

- 1 1 time
- 2 2 to 5 times
- 3 5 or more times
- 97 Don't Know
- 98 Refuse to Answer

J13. In the 6 months before your donation, have you had a manicure or pedicure at a beauty salon or had a shave at a barber shop? (Choose one)

- 0 No
- 1 Yes
- 97 Don't Know
- 98 Refuse to Answer

J14a. Have you been circumcised? (Ask of men only – should we make this not gender specific?)

- 0 No **Skip to J17**
- 1 Yes
- 97 Don't Know
- 98 Refuse to Answer

J15b. At what age were you circumcised?

---

- 97 Don't Know
- 98 Refuse to Answer

J15c. Was your circumcision performed in the 6 months before your donation?

- 0 No
- 1 Yes
- 97 Don't Know
- 98 Refuse to Answer

J15d. Was the circumcision performed in hospital?

- 0 No
- 1 Yes **Skip to J17**
- 97 Don't Know
- 98 Refuse to Answer

J15e. Who performed the circumcision performed?

- 0 General practitioner in doctor's room
- 1 Traditional surgeon/healer using old methods
- 2 Traditional surgeon/healer using new methods (using sterile techniques)
- 97 Don't know
- 98 Refused to Answer

J16a. (*If female (B2=2)*) In the 6 months before your donation, how often have you used anything to dry, clean, or tighten your vagina before or after having sex?

- 1 Every time
- 2 Some times
- 3 Once
- 4 Never **Skip to J17**
- 5 Not Applicable, did not have vaginal sex in the 6 months before my donation **Skip to J17**
- 97 Refused to answer **Skip to J17**

J16b. Please check all the things that you have used to dry, clean or tighten your vagina.

- 1 Water
- 2 Ice

- 3 Soap
- 4 Douche
- 5 Detergents
- 6 Disinfectants
- 7 Acids
- 8 Salt
- 9 Herbs/snuff
- 10 Medications
- 11 Cloth
- 12 Paper
- 13 Tissues
- 14 A gel used as part of a research study
- 15 Other (please specify); \_\_\_\_\_

J17a. In the 6 months before your donation, how often have you used anything to dry, clean, or tighten your anus before or after having sex?

- 1 Every time
- 2 Some times
- 3 Once
- 4 Never **Skip to J25**
- 5 Not Applicable, did not have anal sex in the 6 months prior to my last donation **Skip to J24**
- 97 Refused to answer **Skip to J25**

J17b. Please check all the things that you have used to dry, clean or tighten your anus before having sex.

- 1 Water
- 2 Ice
- 3 Soap
- 4 Douche
- 5 Herbs/snuff
- 6 A gel used as part of a research study
- 7 Other (please specify); \_\_\_\_\_

J18a. In the 6 months before your donation, have you had Raatib, ritual scarring, ritual piercing, ritual circumcision, blood sharing or been stabbed?

- |    |                  |                    |
|----|------------------|--------------------|
| 0  | No               | Skip to J20 |
| 1  | Yes              |                    |
| 97 | Don't Know       |                    |
| 98 | Refuse to Answer |                    |

J18b. Can you please tell us which activity? (Check all that apply)

- 1 Raatib
- 2 Ritual scarring
- 3 Ritual piercing
- 4 Ritual circumcision
- 5 Blood sharing
- 6 Been stabbed
- 7 Other (please specify); \_\_\_\_\_

J19. What was the reason for the activity?

- 1 Cultural, ritual, religious
- 2 Administering a substance in my skin for treatment or prevention
- 3 Letting out blood
- 4 Sealing a "blood pact"
- 5 Other

97 Don't Know

98 Refuse to Answer

J20. In the 6 months before your donation, did you visit a traditional healer and receive traditional medicine other than cuts and/or scarification?

0 No

1 Yes

97 Don't Know

98 Refuse to Answer

J21. In the 6 months before your donation, did you live in an environment where you were frequently bitten by mosquitos?

0 No

1 Yes

97 Don't Know

98 Refuse to Answer

J22. In the 6 months prior to your last donation, did you live in an environment where you were frequently bitten by bed bugs or lice?

- 0 No
- 1 Yes
- 97 Don't Know
- 98 Refuse to Answer

J23. In the 6 months prior to your last donation, did you have an injury such as a knife or stab wound or were you in an accident where you lost blood from a cut or injury?

- 0 No
- 1 Yes
- 97 Don't Know
- 98 Refuse to Answer

**READ and HEARD:** Now, we would like to know about any personal contact you have had with persons who have HIV or hepatitis. In each question, please include only family members, personal friends or acquaintances. (If you are a health care worker, please do NOT include any individuals you have given professional care to, we will ask about those contacts in a minute).

J31. How many people do you personally know who do NOT have AIDS, but have tested positive for HIV, the virus that causes AIDS? (Choose one)

- 0      0 (none)
- 1      1
- 2      2 to 4
- 3      5 or more
- 97     Don't Know
- 98     Refuse to Answer

J32. How many people do you personally know who currently have AIDS or have died of AIDS? (Choose one)

- 0      0 (none)
- 1      1
- 2      2 to 4
- 3      5 or more
- 97     Don't Know
- 98     Refuse to Answer

J33. How many people do you personally know who have hepatitis? (Choose one)

- 0 0 (none)
- 1 1
- 2 2 to 4
- 3 5 or more
- 97 Don't Know
- 98 Refuse to Answer

J34. How many people do you personally know who have died of hepatitis? (Choose one)

- 0 0 (none)
- 1 1
- 2 2 to 4
- 3 5 or more
- 97 Don't Know
- 98 Refuse to Answer

J35. In the 6 months have you been in close contact with anybody who had Hepatitis (yellow jaundice), e.g. people you live or work with?

- 0 No
- 1 Yes
- 97 Don't Know
- 98 Refuse to Answer

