#### **4. Objectives**

1a: To identify the demographic and behavioural risk factors associated with incident HIV infection (based on “NAT yield” or LAg Avidity testing) among blood donors in South Africa.

Hypotheses: 1) The risk factors for incident HIV in blood donors in South Africa will include a recent change in sexual partner, older male/younger female sexual partnership, a greater number of recent sexual partners, unprotected receptive anal intercourse, and lower socioeconomic status.

1b: To identify the demographic and behavioural risk factors associated with incident HBV infection among blood donors in South Africa identified as “NAT-yields” or concordant serology and NAT positive and anti-HBc negative.

Hypotheses: 1) The risk factors for incident HBV in blood donors in South Africa will include greater number of recent sexual partners, recent scarification/tattoo/body markings, and history of personal contact with an HBV-infected person.

2a: To determine HIV subtype and drug resistance profiles among HIV positive donors with recently acquired infection based on year of donation and site of collection, and examine findings with donor demographics and risk behaviors derived in Objective 1.

Hypotheses: 1) The proportion of donors identified with incident HIV infection containing drug resistance mutations will be positively related to the proportion of HIV-positive individuals receiving anti-retroviral therapy at a population-level in South Africa

2b: To determine HBV genotype profiles among HBV positive donors with recently acquired infection based on year of donation and site of collection, and correlate findings with donor demographics and risk behaviors derived in Objective 1

Hypotheses: 1) Incident HBV infections will show differences in genotypes with genotype E increasing when compared to public health data on prevalent infections.

3: To prospectively characterize the virology, immunology and natural history of incident HIV infection among a cohort of recently infected blood donors and a small group of elite controllers in South Africa.

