***READ and HEARD: The next set of questions is about your FOURTH sexual partner, BEFORE your blood donation.***

***READ and HEARD: The next set of questions is about your FIFTH sexual partner, BEFORE your blood donation.***

**SECTION G - SEXUAL PARTNER RISKS**

*If E2a is equal to 0 and E3a is equal to 0 and B1 is equal to 1, then skip to Section H.*

*If E2a is equal to 0 and E3a is equal to 0 and B1 is equal to 2, then skip to Section H.*

**READ and HEARD:** Now, we want to ask about some of the behaviors of the people you have had sex with and your sexual partners. As before when answering, please consider only the following activities, whether or not a condom or other protection was used:

1. *Vaginal sex (contact between penis and vagina)*
2. *Oral sex (mouth or tongue on someone's vagina, penis, or anus)*
3. *Anal sex (contact between penis and anus)*

**You may not know the answers to these questions. Please answer these questions to the best of your knowledge. Several of the questions refer to the period of time in the "six months before your blood donation". This means before your most recent blood donation.**

G1a. To the best of your knowledge, have you ever had sex with anyone who was an injection drug user? (Choose one)

- |    |                  |                    |
|----|------------------|--------------------|
| 0  | No               | Skip to G2a |
| 1  | Yes              |                    |
| 97 | Don't Know       |                    |
| 98 | Refuse to Answer |                    |

G1b. In the 6 months before your donation, have you had sex with anyone who was an injection drug user? (Choose one)

- |    |                  |
|----|------------------|
| 0  | No               |
| 1  | Yes              |
| 97 | Don't Know       |
| 98 | Refuse to Answer |

G2a. To the best of your knowledge, have you ever had sex with anyone who tested positive for HIV? (Choose one)

- 0 No **Skip to instruction before G4a**
- 1 Yes
- 97 Don't Know
- 98 Refuse to Answer

G2b. In the 6 months before your donation, have you had sex with anyone who tested positive for HIV? (Choose one)

- 0 No
- 1 Yes
- 97 Don't Know
- 98 Refuse to Answer

G3a. To the best of your knowledge, have you ever had sex with a man who has had sex with another man? (Choose one)

- 0 No **Skip to G4a**
- 1 Yes
- 97 Don't Know
- 98 Refuse to Answer

G3b. In the 6 months before your donation, have you had sex with a man who has had sex with another man? (Choose one)

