**SECTION H - ALCOHOL AND DRUG USE**

**READ and HEARD:** Now we are going to ask you some general questions regarding alcohol and drug use. Some types of alcohol or drug use can be related to the risk of becoming infected with HIV or HBV. Once again, the following questions are intended to help us determine how to improve the safety of donated blood. We are asking you to respond as truthfully as you can. The answers are confidential. Your individual responses will not be known by SANBS. Your answers will be reported together with all other people who complete the questionnaire.

H1. How often do you drink beer, wine, liquor, or mixed drinks? (Choose one)

- |    |                             |                   |
|----|-----------------------------|-------------------|
| 0  | Never                       | Skip to H4 |
| 1  | 1-3 times per month or less |                   |
| 2  | 1-2 times per week          |                   |
| 3  | 3-6 times per week          |                   |
| 4  | Everyday                    |                   |
| 97 | Don't Know                  |                   |
| 98 | Refuse to Answer            |                   |

H2. On average how many drinks do you have each time you drink? (When answering, one drink is a glass of wine or a beer or a mixed drink.)

Number of drinks         

997 Don't Know

H3a. Have you ever used dagga, marijuana, or hashish? (Choose one)

- |    |                  |                    |
|----|------------------|--------------------|
| 0  | No               | Skip to H4a |
| 1  | Yes              |                    |
| 97 | Don't Know       |                    |
| 98 | Refuse to Answer |                    |

H3b. When was the first year you used dagga, marijuana or hashish?

— — — — YYYY

2097 Don't Know (Year)

2098 Refuse to Answer (Year)

***If H3b is less than B2 then READ and HEARD: "The year that you entered for first year of dagga, marijuana, or hashish drug use is smaller than the year you were born. Please correct the year of your first dagga, marijuana, or hashish drug use." (Returns to H3b)***

H3c. When was the last year you used dagga, marijuana or hashish?

— — — — YYYY

2097 Don't Know (Year)

2098 Refuse to Answer (Year)

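### Skip rules at J17a point to items that do not exist and, followed forward, would limit the only ritual-scarring question to a subgroup selected on sexual practice

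*Protocol*

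**What the plan says.** Protocol, Appendix 7, Section J. J17a has three answers with skips: "4 Never Skip to J25", "5 Not Applicable, did not have anal sex in the 6 months prior to my last donation Skip to J24" and "97 Refused to answer Skip to J25". The other three answers (every time, some times, once) carry no skip and lead through J17b to the next item: "J18a. In the 6 months before your donation, have you had Raatib, ritual scarring, ritual piercing, ritual circumcision, blood sharing or been stabbed". The items then run to J23, and the next printed item is J31.

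Protocol, section 4 (Objectives). The Objective 1b hypothesis names "recent scarification/tattoo/body markings, and history of personal contact with an HBV-infected person" among the expected risk factors. Sections 4.8 and 4.8.1 base HBV power on scarification together with other body modification such as tattoo and piercing, with 150 cases and 450 controls in Table 9.

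Three other instructions in Appendix 7 matter here:
- Section G: the first answer at G2a (ever had a partner who tested positive for HIV) reads "No Skip to instruction before G4a".
- Section H: the item "H1. How often do you drink beer, wine, liquor, or mixed drinks? (Choose one") sends Never to H4.
- Section J: the item "J16a. (*If female (B2=2)*) In the 6 months before your donation" uses B2 as its filter, although B2 is birth year and gender is B1.

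**The concern.** J18a/J18b is the only place where ritual scarring is asked. J20, on traditional healers, expressly leaves out cuts and scarification. If the J17a skips are programmed to the next later item, scarring is recorded only for people who report a particular practice around anal sex. Nothing about scarring justifies that restriction, and the resulting subgroup is selected on behaviour that may itself be related to infection.

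The missing-data plan in section 4.9 (weighting and/or multiple imputation) does not reliably rescue this. Weighting needs some chance of observing the item at each level of the variable that drives missingness. Here J17a drives it completely, and for three of its answers that chance is zero. Imputation would have to extrapolate from the selected subgroup to everyone else with no data to check it.

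The G2a and H1 skips cause smaller losses of the same kind. A respondent who says No about an HIV-positive partner is not asked about male partners who have sex with men, and a non-drinker is not asked about dagga.

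**Working it through.** **1. Routing through Section J.** J14a No and J15d Yes go to J17. Answers 4, 5 and 97 at J16a go to J17, and its other answers reach J17a through J16b. So every route arrives at J17a.

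| J17a answer | Printed next step | J18a to J23 asked? |
|---|---|---|
| Every time, some times, once | J17b, then J18a | Yes |
| Never | J25 (not printed) | No, if resolved forward |
| No anal sex in 6 months | J24 (not printed) | No, if resolved forward |
| Refused | J25 (not printed) | No, if resolved forward |

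J18a to J23 lie between J17 and the numbers J24 and J25. The next later item that exists is J31.

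**2. What is still collected.** Tattoos (J5 to J7) and piercings (J8 to J10) come before J17a. The items on personal contact with hepatitis (J33 to J35) come after J31. Neither group is lost under this routing.

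**3. Reproducing Table 9.** Inputs from section 4.8.1: two-sided alpha 0.05, 150 cases, 450 controls. The direct odds ratio is [p1/(1−p1)]/[p0/(1−p0)], with p1 for cases and p0 for controls. The mean simulated odds ratio is over 20,000 unclustered samples.

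| Control p0 | Case p1 | Direct OR | Mean simulated OR | Table 9 | Unclustered power |
|---|---|---|---|---|---|
| 0.45 | 0.60 | 1.833 | 1.872 | 1.87 | 0.893 |
| 0.50 | 0.65 | 1.857 | 1.898 | 1.90 | 0.898 |
| 0.55 | 0.70 | 1.909 | 1.958 | 1.96 | 0.909 |

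The stated odds ratios reproduce, and power is above 0.80 before any allowance for clustering. The protocol gives no value for the cluster correlation, so it is not modelled.

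Power is Φ[(|p1−p0| − 1.96·SE0)/SE1], with SE0 = √[p̄(1−p̄)(1/n1+1/n0)] and SE1 = √[p1(1−p1)/n1 + p0(1−p0)/n0]. For the first row p̄ = (150×0.60 + 450×0.45)/600 = 0.4875, SE0 = 0.0471 and SE1 = 0.0464. The argument is (0.15 − 1.96×0.0471)/0.0464 ≈ 1.24, which gives 0.893.

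**4. Ritual scarring alone under the printed skips.** Let f be the share of participants who give one of the three answers without a skip. The documents do not give f, so a range is shown, taken as equal in cases and controls. The Table 9 proportions are kept for illustration.

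| f (assumed) | Cases asked (150f) | Controls asked (450f) | Unclustered power, three rows |
|---|---|---|---|
| 5% | about 8 | about 23 | about 0.10 |
| 10% | 15 | 45 | 0.16 to 0.17 |
| 20% | 30 | 90 | 0.29 |
| 50% | 75 | 225 | 0.62 to 0.63 |
| 75% | about 113 | about 338 | 0.79 to 0.81 |
| 100% | 150 | 450 | 0.89 to 0.91 |

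About three quarters of participants would have to reach J18a to keep power near 0.80.

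**5. G2a, H1 and J16a.** At G2a only No carries a skip, and its target lies beyond G3a and G3b. Yes, Don't Know and Refuse all continue to G3a. At H1, Never passes over H2 (drinks per occasion, reasonably) and also H3a to H3c (dagga). At J16a the filter says female in words but cites the birth-year item.

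**The case against.** The strongest reply is that J24 and J25 are dead references. A programmer must resolve them before the ACASI can run, and stale numbering is the likely cause. The appendix is visibly unfinished: J14a and L5 carry open drafting questions, and the OMB number is a placeholder. Section 4.11 plans pilot testing of the ACASI before enrollment. This stands to the extent that the loss of J18a to J23 depends on how the reference is resolved. It does not remove the fault. Section 4.4.1 names Appendix 7 as the questionnaire content, no other text gives the right target, and a forward skip produces no visible error when the instrument runs.

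Four stronger readings are tempting, and the documents do not support them:
- A reader might infer that the exposure behind HBV power is missing for nearly everyone. That exposure is a composite, and its tattoo and piercing parts are asked before J17a.
- A reader might infer that almost all participants are affected. That is plausible, but no frequency of J17a answers is given.
- A reader might infer that G3 is asked only of people with a known HIV-positive partner. Those answering Don't Know or Refuse at G2a are asked too, and for men sex with men is also captured at E3a and F3.
- A reader might infer that no woman is asked J16a. The filter states its intent in words, so B2 is a mislabel for B1.

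**Conclusion.** The routing is wrong as printed and needs correction before use. If the J17a skips are resolved forward, ritual scarring is seen only in a subgroup selected on sexual practice, and the composite body-modification exposure for Objective 1b becomes incomplete and misclassified. For ritual scarring on its own, unclustered power for the Table 9 differences would be about 0.10 to 0.29 if 5% to 20% reach J18a, against 0.89 to 0.91 if all are asked. Those figures rest on the assumed share, on equal shares in cases and controls, on the Table 9 proportions applying to scarring alone, and on no clustering. The routing fault itself rests on none of them.

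The G2a and H1 skips are real but lesser faults: G3 is lost for those who answer No at G2a, and dagga, which is not a named hypothesis, is lost for non-drinkers. J16a is a labelling error.

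**What to change.** Before the ACASI is locked:
- Point the never, not-applicable and refused answers at J17a to J18a, and remove the references to J24 and J25.
- Point the No answer at G2a to G3a.
- Point the Never answer at H1 to H3a.
- Change the J16a filter label from B2=2 to B1=2.
- In the pilot testing already planned, run scripted respondents through every branch and confirm that each reaches J18a, G3a and H3a where intended.

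This changes six printed instructions and adds no questions or participants. More respondents will answer existing items, so interviews lengthen slightly. Section 4.6 allows up to nine months for OMB clearance of the instruments, so the correction is best made before submission.

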## **4.8 Statistical Considerations**

To estimate the required sample size for the incident HIV and incident HBV groups and the control negative donors we focused on two different behaviors that have been separately associated with HIV and HBV infection in South Africa. For HIV infection we considered the risk factor of multiple sexual partners. For HBV we assumed scarification or other forms of body modification would be a potential route for HBV acquisition. Power analyses below indicate that with expected enrollment we will have sufficient power to detect odds ratios between 1.6 and 2.0 for putative incident HIV and HBV risk factors.

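### The only scarring item, J18a, is narrower than its follow-up J19 and than J20 presumes, so cuts made by a traditional healer for treatment or protection can go unrecorded in the HBV analysis

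*Protocol*

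**What the plan says.** Protocol section 4 (Objective 1b) names "recent scarification/tattoo/body markings" among the hypothesised risk factors for incident HBV. Section 4.8 sizes the HBV comparison on the same kind of exposure: "For HBV we assumed scarification or other forms of body modification would be a potential route for HBV acquisition". The HBV power text in section 4.8.1 groups scarification with tattooing and piercing. None of these passages limits scarification to ritual practice.

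In the questionnaire (Appendix 7, Section J), scarring appears in one question stem, J18a: "have you had Raatib, ritual scarring, ritual piercing, ritual circumcision, blood sharing or been stabbed". A No goes straight to J20. Other respondents see J18b, which asks which activity it was and has a free-text option, and J19, which asks the reason. J19 has one option for cultural, ritual or religious reasons and a separate one for "Administering a substance in my skin for treatment or prevention". J20 then asks "did you visit a traditional healer and receive traditional medicine other than cuts and/or scarification".

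Elsewhere, I12 asks "did you receive an injection from a traditional healer for any reason", and J23 asks about injuries and accidents with blood loss. Recent tattoos (J6) and recent piercings (J9) have items of their own.

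**The concern.** The three items do not fit together. J19 shows that the authors meant to record skin procedures done for treatment or prevention and regarded them as different from ritual. J20 leaves out healer cuts and scarification, which makes sense only if an earlier question has covered them. The only earlier question is J18a, and its stem mentions ritual scarring alone, in a list with Raatib, blood sharing and being stabbed.

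An exposure screened out at a gate question is not in the data, so no later analysis can restore it. Nor can the loss be made up with more cases. Section 4.8.1 expects at best about 100 recent HBV infections a year and about 50% participation, so three years give 100 × 0.5 × 3 = 150, which is the whole target.

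**Working it through.** **Step 1: follow one donor through the items.** Take a donor whom a traditional healer cut for treatment or protection within six months of donating, and who does not regard this as ritual. Assume the donor reaches J18a.

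- I12 (healer injection): No, because a cut is not an injection.
- J6 and J9 (recent tattoo, recent piercing): No, unless the donor also has one.
- J18a: a truthful No, because the stem names only ritual scarring and the other listed activities do not apply.
- J18b and J19: not shown after a No.
- J20: the cuts must be left out, by its own wording.
- J23: No, because this was neither an injury nor an accident.

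The donor's record then shows no scarification. If the same donor answers Yes, Don't Know or Refuse at J18a, no skip applies, and the free-text option in J18b and the treatment option in J19 are both open. The gap is therefore at the gate.

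**Step 2: reproduce the plan's figures.** Table 9 gives control and case proportions with 450 controls and 150 cases. The odds ratio is [p1/(1−p1)] / [p0/(1−p0)].

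| Control p0 | Case p1 | OR from proportions | OR in Table 9 | Power, independent samples |
|---|---|---|---|---|
| 0.45 | 0.60 | 1.83 | 1.87 | 89% |
| 0.50 | 0.65 | 1.86 | 1.90 | 90% |
| 0.55 | 0.70 | 1.91 | 1.96 | 91% |

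The plan states 80% power from a clustered simulation whose correlation is not given, so it cannot be reproduced exactly. A design effect of about 1.3 would bring these powers to 80–82%. The figures below use independent samples and serve only for comparison with each other.

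**Step 3: illustrate under-capture.** Assume that the same sensitivity s applies to cases and controls and that there are no false positives. The observed proportions are then s·p1 and s·p0. Power = Φ[(d − 1.96·SE0)/SE1], where d is the difference in observed proportions, SE0 uses the pooled proportion and SE1 the separate ones.

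Middle row, s = 1: d = 0.15, pooled proportion (97.5 + 225)/600 = 0.5375, SE0 = 0.0470, SE1 = 0.0455, z = (0.15 − 0.0921)/0.0455 = 1.27, power 90%.

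| s | Case | Control | OR | Power |
|---|---|---|---|---|
| 1.00 | 0.650 | 0.500 | 1.86 | 90% |
| 0.90 | 0.585 | 0.450 | 1.72 | 82% |
| 0.75 | 0.4875 | 0.375 | 1.59 | 68% |

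**Step 4: what s stands for.** The exposure is a composite, so a donor is lost only if scarification is the sole qualifying exposure and it is missed. Then s = 1 − f·m, where f is the share of exposed donors with scarification only and m is the share of those missed. With m = 0.5, f = 0.2 gives s = 0.90 and f = 0.5 gives s = 0.75. Both f and m are assumptions; the documents give neither.

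**The case against.** The case against has real force on four points.

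First, a reader might infer that treatment cuts are asked about nowhere. The documents do not support that. J19 has an explicit option for them, J18b has a free-text field, and only a No closes the route. The block was meant to capture such cuts and will capture some.

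Second, a reader might infer that these donors are counted as unexposed in the HBV hypothesis. The protocol does not say how the exposure variable is derived, and that may properly be left to the analysis plan. The hypothesised exposure also includes tattoos and body markings, so a donor missed at J18a can still be exposed through another item.

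Third, it is tempting to apply a large miss rate to the whole Table 9 proportion. On the same method, missing 50% or 75% of all exposure would give power of about 44% or 23%. Those figures treat every exposed donor as scarified only, which the section 4.8.1 definition contradicts.

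Fourth, how donors understand ritual scarring is an empirical matter. Section 4.11 plans pilot testing of the ACASI, and the questionnaire still carries drafting notes, so the wording may yet change.

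These points limit the size of the problem without removing the mismatch. J18a remains narrower than J19 and than J20 presumes. Pilot testing may expose this, but nothing in the protocol directs it there.

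**Conclusion.** The point holds as an inconsistency between questionnaire items. Treatment or protective cuts are named in no question stem. A donor who does not call them ritual can pass through the questionnaire with no record of scarification, and J20 adds to this by telling the donor to leave them out.

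If cases and controls are affected alike, the scarification odds ratio tends toward 1 and treatment cuts are incompletely measured. If they read the stem differently, the direction of bias is not determined. The size cannot be derived from the documents. The illustration (odds ratio 1.72 or 1.59 and power 82% or 68%, at overall sensitivity 0.90 or 0.75) rests on equal sensitivity in both groups, no false positives, no clustering and an assumed scarification-only share. It does not show that the HBV comparison is underpowered. The correction is worth making because it is cheap now and impossible after data collection.

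**What to change.** Before the ACASI is programmed, take scarification out of J18a and give it its own item. A possible wording: *In the 6 months before your donation, did anyone, including a traditional healer, cut, scratch or scar your skin for any reason, such as ritual, culture, treatment or protection?* Follow a Yes with J19. Keep the remaining J18a activities in a separate item. J20's exclusion of cuts and scarification is then justified, and the three items agree. Use the new item as the scarification component when the Objective 1b exposure is defined.

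The cost is one reworded item, one added yes/no question and a few seconds of interview time.
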